## 2 Study objectives and endpoints

### 2.1 Objectives and related endpoints

**Table 2-1 Objectives and related endpoints**

Objective(s)	Endpoint(s)
Primary Objective(s)	Endpoint(s) for primary objective(s)

 
To assess the safety/tolerability of 52 weeks of treatment with QMF149 (150/320 µg, once daily) in Japanese patients with inadequately controlled asthma.
 
	
 
The incidence and severity of treatment emergent adverse events (AEs) over 52 weeks of treatment
 

Secondary Objective(s)	Endpoint(s) for secondary objective(s)

 
To assess the safety of QMF149 over 52 weeks of treatment
 
To assess the efficacy of QMF149 in terms of lung-function in Japanese patients with inadequately controlled asthma.
 
To assess the efficacy of QMF149 in terms of asthma control.
 
	
 
ECG, vital sign (blood pressure, pulse rate), laboratory parameters (hematology, clinical chemistry and urinalysis), plasma cortisol over 52 weeks of treatment
 
Change from baseline of pre-dose FEV1 measured after 26 and 52 weeks treatment
 
Change from baseline of morning and evening PEF during 52 weeks treatment
 
Change from baseline of ACQ-7 after 26 and 52 weeks treatment
 
Responder rate of patients achieving the minimal important difference (MID) of ACQ-7 ≥ 0.5 after 26 and 52 weeks treatment
 

1) To assess the efficacy of QMF149 in terms of rescue medication use	1. Change from baseline of rescue medication use during 52 weeks treatment

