**Table 6-1 Assessment schedule**

Epoch	Screening			Treatment											EOT Early treatment discontinuation	PSW Early Study Discontinuation	Follow -up 
	1	2	99	101	102	103	104	105	106	107	108	109	110	111			
Visit number	C	C	C	C	C	T	C	T	T	C	T	C	T	C	C	T	T
Clinic (C) / Telephone (T)	C	C	C	C	C	T	C	T	T	C	T	C	T	C	C	T	T
Week	-4 to -2	-2	0	0	4	8	12	16	20	26	32	36	44	52			56
Obtain informed consent	X																
Relevant Medical History /Demographics	X																
History of Asthma exacerbation	X																
Smoking History	X																
Current asthma medication review	X																
Inclusion/ Exclusion criteria	X	X	X														
Central pregnancy test (Serum)		X												X	X		
Local pregnancy test (urine)			X							X							
Urinalysis (dipstick)			S							S				S	S		
Hematology/ biochemistry		X		X						X				X	X		
Evening plasma cortisol				X						X				X	X		
Inhalation device training			S														
Drug dispensing				X	X		X			X		X					
Administer study drug at the visit				X			X			X				X			
Reversibility test		X															
Spirometry (centralized)		X		X			X			X				X	X		
Issue and training on patient eDiary	S			S													
Device training, e-Diary, ePEF	S	S	S														
Prior and Concomitant non-indication Medications	X	X	X	X	X	X	X	X	X	X	X	X	X	X	X	X	X

Epoch	Screening			Treatment													Follow-up 
	1	2	99	101	102	103	104	105	106	107	108	109	110	111	EOT Early treatment discontinuation	PSW Early Study Discontinuation	
Clinic (C) / Telephone (T)	C	C	C	C	C	T	C	T	T	C	T	C	T	C	C	T	T
Week	-4 to -2	-2	0	0	4	8	12	16	20	26	32	36	44	52			56
Prior and Concomitant Asthma Medications	X	X	X	X	X	X	X	X	X	X	X	X	X	X	X	X	X
Review and upload patient eDiary			S		S		S			S		S		S	S		
ACQ-7		X		X			X			X				X	X		
Physical examination		S		S	S		S			S		S		S	S		
Oropharyngeal examination		S		S	S		S			S		S		S	S		
Vital sign: BP and pulse		X		X	X		X			X		X		X	X		
Record height and weight		X															
ECG		X		X						X				X	X		
SAE recording	X	X	X	X	X	X	X	X	X	X	X	X	X	X	X	X	X
AE recording	X	X	X	X	X	X	X	X	X	X	X	X	X	X	X	X	X
Review surgery and Procedures	X	X	X	X	X	X	X	X	X	X	X	X	X	X	X	X	X
Record healthcare visits for asthma worsening					X	X	X	X	X	X	X	X	X	X	X	X	
Survival status																X	X
Study Disposition (Screening)		X	X														
Study Disposition (Study Phase Completion)														X	X	X	
Record End of Treatment page														X	X	X	
Study Disposition (Follow-up)																	X

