Early Study Discontinuation Visit should be used for Premature study withdrawal (PSW, please refer to [Section 5.6.2](#))

X = assessment to be recorded on clinical data base

S = these assessments are source documentation only and will not be entered into the eCRF

 Information about patients' survival will be obtained by a telephone call during the study treatment period and 30 days after the patient's last dose of study drug for completed patients. For patients who withdraw early, please refer to discontinuation of study treatment and premature patient withdrawal section.

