**Table 6-2 Timing of clinic visit procedures**

	Time Point 	ACQ-7	ECG	Vital Signs 	Hematology Chemistry /Plasma cortisol/Urinalysis 	Spirometry 
Visit 99/ Visit 101 Day 1	-50 min	X				
	-45 min					X
	-30 min		X	X	X	
	-15 min					X
	30 min		X			
Visit 104 Week 12	-50 min	X				
	-45 min					X
	-30 min			X		
	-15 min					X
Visit 107 Week 26	-50 min	X				
	-45 min					X
	-30 min		X	X	X	
	-15 min					X
Visit 111 Week 52 Day 365	-50 min	X				
	-45 min					X
	-30 min		X	X	X	
	-15 min					X

1 Time relates to the dose given from the device at visit. When multiple measurements are scheduled at a single time-point, they should be done wherever possible in the following order: ECG, vital signs and then samples for hematology/clinical chemistry/plasma cortisol and urinalysis.

2 Systolic and diastolic blood pressure and heart rate (radial pulse).

3 Urine analysis at central laboratory is to be done only if the urine dipstick is abnormal, and only done pre-dose.

4 A minimum 10 min rest period from the end of spirometry maneuvers and the beginning of ECG assessments must be observed at all times.

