#### **6.5.4.3 Urinalysis**

Dipstick measurements for specific gravity, pH, protein, glucose and blood will be performed at Visits 99, 107, 111, and EOT if applicable. Dipsticks are provided to investigators from the central laboratory.

If dipstick test is abnormal, the sample will be sent to central laboratory for additional testing, including assessment of microscopy and WBC and RBC sediments. The Central Laboratory will provide detailed procedures for the preparation and collection of these samples in the laboratory manual.

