## 8.3 Database management and quality control

Novartis staff review the data entered into the CRFs by investigational staff for completeness and accuracy and instruct the site personnel to make any required corrections or additions. Queries are sent to the investigational site using an electronic data query. Designated investigator site staff is required to respond to the query and confirm or correct the data. If the electronic query system is not used, a paper Data Query Form will be faxed to the site. Site personnel will complete and sign the faxed copy and fax it back to Novartis staff that will make the correction to the database. The signed copy of the Data Query Form is kept at the investigator site.

Concomitant medications entered into the database will be coded using the WHO Drug Reference List, which employs the Anatomical Therapeutic Chemical classification system. Concomitant procedures, non-drug therapies and adverse events will be coded using the Medical dictionary for regulatory activities (MedDRA) terminology.

Laboratory samples will be processed centrally and the results will be sent electronically to Novartis.

ECG readings will be processed centrally and the results will be sent electronically to Novartis.

Spirometry readings will be processed centrally and the results will be sent electronically to Novartis.

Diary data will be entered into an electronic diary by the patient. The system will be supplied by a vendor(s), who will also manage the database. The database will be sent electronically to Novartis personnel.

Data about all study drug(s) dispensed to the patient and all dosage changes will be tracked using an Interactive Response Technology (IRT). The system will be supplied by a Novartis IRT, who will also manage the database. The database will be sent electronically to Novartis.

The occurrence of relevant protocol deviations will be determined. After these actions have been completed and the database has been declared to be complete and accurate, it will be locked and made available for data analysis. Any changes to the database after that time can only be made after written agreement by Novartis Development management.

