1.2 Study objectives and endpoints

Objective(s)	Endpoint(s)
Primary Objective(s) 
To assess the safety/tolerability of 52 weeks of treatment with QMF149 (150/320 µg, once daily) in Japanese patients with inadequately controlled asthma.	Endpoint(s) for primary objective(s) 
The incidence and severity of treatment emergent adverse events (AEs) over 52 weeks of treatment
Secondary Objective(s) 
To assess the safety of QMF149 over 52 weeks of treatmentTo assess the efficacy of QMF149 in terms of lung-function in Japanese patients with inadequately controlled asthma.	Endpoint(s) for secondary objective(s) 
ECG, vital sign (blood pressure, pulse rate), laboratory parameters (hematology, clinical chemistry and urinalysis), plasma cortisol over 52 weeks of treatmentChange from baseline of pre-dose FEV₁ measured after 26 and 52 weeks treatmentChange from baseline of morning and evening PEF during 52 weeks treatment

Objective(s)	Endpoint(s)

To assess the efficacy of QMF149 in terms of asthma control.	
Change from baseline of ACQ-7 after 26 and 52 weeks treatmentResponder rate of patients achieving the minimal important difference (MID) of ACQ-7 ≥ 0.5 after 26 and 52 weeks treatment

To assess the efficacy of QMF149 in terms of rescue medication use	
Change from baseline of rescue medication use during 52 weeks treatment

2 Statistical methods

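### The planned urinalysis tables would cover only abnormal-dipstick samples, and a patient normal at Visit 99 would have no databased baseline

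*Protocol*

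**What the plan says.** **Endpoint.** Protocol Table 2-1 names, under the secondary safety objective, "laboratory parameters (hematology, clinical chemistry and urinalysis), plasma cortisol over 52 weeks of treatment". SAP 1.2 repeats this.

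**Collection.** Protocol 6.5.4.3 states: "Dipstick measurements for specific gravity, pH, protein, glucose and blood will be performed at Visits 99, 107, 111, and EOT if applicable". In Table 6-1 the dipstick row is coded S at each of these visits and is blank at Visit 2. The footnote defines the code: "S = these assessments are source documentation only and will not be entered into the eCRF".

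**Central testing.** Table 6-2 footnote 3: "Urine analysis at central laboratory is to be done only if the urine dipstick is abnormal, and only done pre-dose". Protocol 6.5.4.3 agrees: "If dipstick test is abnormal, the sample will be sent to central laboratory for additional testing". It gives microscopy and white and red cell sediment as examples of that testing.

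**Route to the database.** Protocol 8.3 describes one laboratory route: "Laboratory samples will be processed centrally and the results will be sent electronically to Novartis".

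**Analysis.** Protocol 9.5.2 plans frequency tables for categorical laboratory parameters and shift tables for every laboratory parameter. SAP 2.7.2 keeps both and fixes a worst-case direction (the maximum) for continuous urinalysis parameters, so urinalysis is meant to be tabulated. Laboratory baseline is the Day 1 pre-dose value. The fallback is Visit 2 or an unscheduled visit before first dose.

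**The concern.** The analysis sections treat urinalysis like hematology and chemistry, where every patient has a central result at every scheduled visit. The collection sections do not deliver that. A normal dipstick has no stated route into the database, so whether a urine record exists depends on the result.

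Two things follow. The by-visit tables would describe a subset selected for abnormality while appearing under a Safety Set heading. The shift a reader of a long-term safety report most wants to see, from normal before treatment to abnormal on treatment, could not be read from them. Protocol 9.7 and SAP 2.13 run all protocol-specified analyses at the Week 26 interim for the initial Japanese submission, so the same tables would appear there first.

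**Working it through.** **1. What each visit leaves in the database, following the text literally**

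| Dipstick at the visit | Entered in eCRF | Central result sent |
|---|---|---|
| Normal | No (S) | No |
| Abnormal | No (S) | Yes |
| Not done | No | No |

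The first and third rows are identical.

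**2. What a Visit 99 to Visit 111 shift table would then hold**

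| Visit 99 | Visit 111 | Baseline record | Week 52 record |
|---|---|---|---|
| Normal | Normal | none | none |
| Normal | Abnormal | none | yes |
| Abnormal | Normal | yes | none |
| Abnormal | Abnormal | yes | yes |

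Only the last pattern gives a complete pair. This holds at any abnormality rate.

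**3. Do other rules fill the gap?**

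- *Baseline fallback (SAP 2.7.2).* Table 6-1 schedules no urinalysis at Visit 2. An unscheduled pre-dose sample could help an isolated patient only.
- *Missing data.* SAP 2.1.1 computes change only where both values exist. SAP 2.7 and 5.1 plan no imputation. The missing category in SAP 2.1 would show the gap in categorical tables but would not separate normal from not done.
- *Deviations.* The table in SAP 2.3.1 has a category for omitted key procedures, but nothing says that a missed dipstick counts.
- *EOT.* SAP 2.1.1 admits discontinuation-visit laboratory data only to notable-value and extreme-value summaries, and such data supply no baseline.
- *Notable values.* SAP 2.7.2 counts a notable value with missing baseline as new, but SAP 5.3 sets no criterion for any urine parameter, so no bias enters there.

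**4. Numbers**

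The plan's own figures reproduce: 100 − 41 = 59 completers; 59 / 0.90 = 65.6, rounded up to 66 treated; 66 / 0.75 = 88 screened. The documents give no abnormality rate p, so the following is purely illustrative, with p assumed equal at both visits:

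| Assumed p | Baseline record, 66p | No baseline record, 66(1 − p) | Complete pairs: 59p² (visits independent) to 59p (full persistence) |
|---|---|---|---|
| 5% | 3.3 | 62.7 | 0.1 to 3.0 |
| 10% | 6.6 | 59.4 | 0.6 to 5.9 |
| 30% | 19.8 | 46.2 | 5.3 to 17.7 |
| 40% | 26.4 | 39.6 | 9.4 to 23.6 |

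**5. Cost of databasing the dipstick**

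The 59 completers have three visits each: 59 × 3 = 177. The 66 − 59 = 7 dropouts have two or three each: 14 to 21. The total is 191 to 198 visit records. At five parameters per record that is 191 × 5 = 955 to 198 × 5 = 990 fields.

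**The case against.** Dipstick first and central testing on abnormality is an ordinary design, and the protocol states it consistently. The analysis is descriptive. Clinically significant findings still become adverse events under Protocol 7.1. The only urinalysis-specific analysis sentence in the SAP is the worst-case direction; the rest is general laboratory wording. The protocol's own rule also implies that an attended visit without a central record had a normal dipstick. All of this stands as a reason to keep the point small. It does not remove it: the implied rule fails for a dipstick not done or a sample not sent, and no analysis rule adopts it. The protocol does database a site urine test when it wants the result, since Table 6-1 codes the local pregnancy test X.

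Three stronger readings are tempting, and the documents do not support them:

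- *That Tables 5-4 and 6-1 contradict each other.* Table 5-4 codes a row of safety laboratory tests that includes urinalysis X at early discontinuation, while Table 6-1 codes the dipstick S at EOT. The X can be read as the central result that follows an abnormal dipstick, so the two are not necessarily in conflict.
- *That a number of lost normal-to-abnormal shifts can be given.* Any such count needs an assumed rate and an assumed persistence, and under full persistence it is zero. It would also count dipstick transitions, which are not cells of a central-result table: an abnormal dipstick may be followed by a normal central result, and the protocol does not say that the five dipstick parameters are repeated centrally.
- *That no other data route exists.* Protocol 6.5.4 sends sample and reporting details to a laboratory manual that is not among the documents.

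**Conclusion.** The mismatch between collection and analysis is real. Carried out as written, the plan yields urinalysis tables restricted to abnormal-dipstick samples, with no databased baseline for patients normal at Visit 99. That conclusion rests on the S coding, on the condition for central testing, and on there being no further route in the laboratory manual.

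The impact is minor. One descriptive component of a secondary safety endpoint is affected. The primary adverse event analysis, hematology, chemistry and cortisol are not. A reader might infer that urinary safety signals would be missed or that the safety conclusion is weakened. The documents do not support that, because clinically significant findings reach the adverse event data whatever happens to the tables. The illustrative counts show how thin the tables could be; they do not measure harm. It is worth correcting because the correction is cheap and the uncorrected tables invite misreading.

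**What to change.** **Preferred.** In Table 6-1, change S to X for the dipstick at Visits 99, 107, 111 and EOT, and enter the result for each of the five parameters in the eCRF, with not done as an option. In SAP 2.7.2:

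- base the urinalysis frequency and shift tables on these results for the Safety Set, with Visit 99 as baseline;
- present the central follow-up results (microscopy, sediment and any continuous values) as a listing only, because the dipstick supplies no baseline for them;
- remove or restrict the continuous urinalysis worst-case summary to match.

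Cost: about 191 to 198 extra visit records copied from results the site already holds, an eCRF page, and a protocol amendment under Protocol 11.1. No new sampling is needed.

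**If the dipstick stays source-only.** In SAP 2.7.2, do one of the following:

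1. replace the urinalysis tables with a listing of central results; or
2. keep the tables but label them as abnormal-dipstick samples only, with the number tested as denominator and no statement about shifts from normal.

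Record the departure from Protocol 9.5.2 in SAP Section 4, which now declares none. Cost: a few sentences in two SAP sections, and giving up any statement about change from normal.

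**Optional.** State whether the urinalysis X in Table 5-4 means the dipstick or the central follow-up result.

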**Table 6-2 Timing of clinic visit procedures**

	Time Point 	ACQ-7	ECG	Vital Signs 	Hematology Chemistry /Plasma cortisol/Urinalysis 	Spirometry 
Visit 99/ Visit 101 Day 1	-50 min	X				
	-45 min					X
	-30 min		X	X	X	
	-15 min					X
	30 min		X			
Visit 104 Week 12	-50 min	X				
	-45 min					X
	-30 min			X		
	-15 min					X
Visit 107 Week 26	-50 min	X				
	-45 min					X
	-30 min		X	X	X	
	-15 min					X
Visit 111 Week 52 Day 365	-50 min	X				
	-45 min					X
	-30 min		X	X	X	
	-15 min					X

1 Time relates to the dose given from the device at visit. When multiple measurements are scheduled at a single time-point, they should be done wherever possible in the following order: ECG, vital signs and then samples for hematology/clinical chemistry/plasma cortisol and urinalysis.

2 Systolic and diastolic blood pressure and heart rate (radial pulse).

3 Urine analysis at central laboratory is to be done only if the urine dipstick is abnormal, and only done pre-dose.

4 A minimum 10 min rest period from the end of spirometry maneuvers and the beginning of ECG assessments must be observed at all times.

## 6.1 Information to be collected on screening failures

All patients/subjects who have signed informed consent but not entered into the next epoch will have the study completion page for the screening epoch, demographics, inclusion/exclusion, and serious adverse event (SAE) data collected. Adverse events that are not SAEs will be followed by the investigator and collected only in the source data.

## 6.2 Patient demographics/other baseline characteristics

Patient demographic and baseline characteristic data to be collected on all patients include:

- Year of birth
- Age
- Sex
- Race and ethnicity

- Height and Weight
- BMI (calculated)
- Baseline physical examination (not databased other than in the context of relevant medical history)
- Vital signs
- ECG
- Date of diagnosis of asthma
- Relevant medical history/ current medical condition present before signing the informed consent
- Smoking history and status
- ACQ-7
- Prior concomitant medication (Both asthma related and non-asthma related)
- Pre and post-bronchodilator spirometry (screening spirometry and reversibility testing).
- Baseline PEF

### **6.3 Treatment exposure and compliance**

The time of study treatment administration at each in-office dosing visit will be collected on the eCRF as well as any dosing interruptions. For assessments where spirometry is performed, the time of dosing is to be taken from the spirometer. While at home, the time of study treatment administration will be recorded by the patient in the e-Diary once a week. The data from the e-Diary will be reviewed at each visit.

Study treatment compliance should be assessed by the investigator and/or center personnel at all visits. In order to ensure compliance and safety follow-up, the patients will be requested to record once per week in the e-diary whether he/she missed any dosage in the evening from Visit 101 to 111. Where necessary, the Investigator will discuss compliance/documentation issues with the patient. The Investigator or designee will collect, from the patient, the used/unused investigational medication and packaging (unused capsules/blister strips and SDDPIs) at Visits 102, 104, 107, 109, 111 (or at Early Treatment Discontinuation/end of treatment Visit (EOT) or Study Withdrawal visit if applicable). Study treatment compliance will be assessed from the capsule count from previously dispensed blister strips for the Concept1.

### **6.4 Efficacy**

#### **6.4.1 Spirometry**

The following spirometric assessments will be made:

- Forced expiratory volume in one second (FEV1)
- Forced Vital Capacity (FVC)

Spirometric assessments will be measured at Visits 2, 101, 104, 107, 111 and EOT if applicable as indicated in [Table 6-1](#).

Pre-dose FEV1 is defined as the mean of the two FEV1 values measured at –45 min and –15 min prior to evening dose taken at the site.

All clinic visits must occur in the evening. Please refer to [Table 6-2](#) for full details of the scheduling of spirometry measurements. Equipment for spirometry assessments will be provided to all study sites by a Central Spirometry vendor, and all measurements will be reviewed by trained spirometry technicians at the central vendor.

Please refer to the latest version of Spirometry Guidance, in [Appendix 3](#) for full details on performing spirometry.

## **6.4.2 Electronic Diary**

All patients will be provided with a patient electronic diary (referred to as eDiary or eDiary/ePEF) to record daily clinical symptoms, peak flow or rescue medication (salbutamol) use. The patients will be instructed to routinely complete the patient diary twice daily – at the same time morning or evening (before taking the study drug) and approximately 12 hours apart. The eDiary is to be reviewed at each clinic visit until study completion. Sites and patients will receive appropriate training and guidance on the use of the eDiary device (see [Appendix 4](#) for questions).

### **6.4.2.1 Number of inhalations of Rescue Medication**

The total number of inhalation used of rescue medication (number of puffs taken in the previous 12 hours) will be recorded morning and evening by the patient, in the eDiary.

The patient will input the number of puffs of rescue medication they have used during the 12 hours previous. The patients mean evening and morning rescue medication usage will be automatically be calculated by the eDiary. This SABA data collected by the patient during the last 7 days of screening will be used to set alerts to the patient to contact the investigator in case of worsening asthma (see [Section 6.4.4](#) Asthma worsening criteria).

